8.0 STUDY PLAN

8.1 Study Procedures

The following sections describe the study procedures and data to be collected. Subjects will be assessed at the screening (Visit 1) and baseline (Visit 4) visits to determine and confirm eligibility. The identified target teeth at the screening visit (Visit 1) will be reconfirmed intra-operatively at the surgery visit (Visit 5), and one eligible tooth will be selected to receive the study treatment. Within 2 months prior to the study treatment, each subject will undergo thorough scaling and planing of all teeth in the target tooth's quadrant to control the disease process and minimize lesion variability (Visit 2 and if necessary, Visit 3). Note that a patient may have already undergone scaling and planing prior to screening. After study treatment, each subject will be monitored at periodic intervals to assess safety and effectiveness for at least six months. The Schedule of Study Procedures is located in Appendix A.

The Investigator and all study personnel will be blinded to the treatment. Only calibrated Examiners who are different from the surgeon performing the implantation should carry out the clinical evaluations to assess the study safety and effectiveness parameters. See Section 8.2 for calibration details.

8.1.1 Informed Consent Procedure

The requirements of the informed consent are described in Section 14.2.

Two informed consents are proposed in this study. Informed consent for screening must be obtained prior to the subject undergoing screening (Visit 1). In addition, those subjects that meet the screening requirements must complete an informed consent for enrollment into the study (Visit 4). A unique subject identification number (subject screening number) will be assigned to each subject at the time that informed consent for screening is obtained. A different, unique subject identification number (subject enrollment number) will be assigned to each subject at the time that informed consent for enrollment is obtained. This subject enrollment number will be used throughout the study.

8.1.2 Clinical Outcomes

The Investigator and other qualified site personnel (i.e. Dentist, Dental Hygienist) will perform the clinical examinations using the following methods at the examination visits. Clinical Measurement will be performed throughout pre-treatment, baseline and post-treatment follow-up visits during the trial. Intra-Surgical Measurement will be performed at Visit 5 only.

Only calibrated North Carolina 15 mm periodontal probes will be used. The measurements will be rounded off to the nearest millimeter (0.5 mm is to be rounded up). Clinical probing measurements will be made at the mid-facial, mesial and distal line angles and at mid-lingual, mesial, distal line angles with a calibrated probe. The measurements will be made at these standard locations to the deepest part of the defect.

Clinical Measurement

- Pocket depth (PD): From free gingival margin to the base of the pocket
- Clinical attachment level (CAL): will be calculated by adding PD and GR.
- Gingival recession (GR): From the free gingival margin to the CEJ

Intra-Surgical Measurement (Visit 5 only)

- Alveolar crest height (ACH): From cemento-enamel junction to alveolar crest (CEJ-AC)
- Base of defect from CEJ (BD): From cemento-enamel junction to the base of osseous defect (CEJ-BD)
- Vertical bone defect depth at its deepest location (vBD): vBD will be calculated by subtracting ACH from BD

8.1.3 Radiologic Outcomes

The radiographic assessments include standardized periapical radiographs using Rinn positioning instruments and thermoplastic impression tabs. One standardized intra-oral periapical radiograph will be obtained at baseline and again at 3 and 6 months. These radiographs should be taken perpendicularly with a standardized long-cone parallel technique and should image the target tooth and at least 2 mm on either side of the osseous defect. The following standardizing technique will produce repeatable diagnostic quality radiographs with close to identical geometry and image clarity.

8.1.3.1 Assemble the needed materials

- A patient-specific reusable bite registration is used as a positioning guide.
- Rinn film holder and positioning apparatus are used to maintain beam direction.
- A digital sensor or a phosphor plate radiography system.
- One image of a current US penny for calibration of the system.

8.1.3.3 Radiographic Image Processing and Outcomes Assessment

[figure not shown]
Coded radiographic images will be sent to the reading center at UAB where they are given a unique identifier and logged into an electronic file. Subsequent images are matched to the identifier and a digit added which identifies the follow-up sequence (i.e. 6, post-baseline).

Baseline images are saved in an electronic study file and linear measurements, in millimeters, of bone height along mesial and/or distal root surfaces of the defect site are captured and entered into a database.

Image processing software is used to capture measurements. First, the image of the penny will be used for the conversion of pixels to millimeters for every system. The number of pixels per millimeter is calculated by dividing the measurement of the penny in pixels by the known diameter of a penny of 19.2 mm. If all parameters of the system stay the same from radiograph to radiograph, the image of the penny should only be submitted once. However, if any parts of the system change (i.e. the sensor or capturing device, scanner or capturing software), a new penny radiograph should be submitted.

Then, measurements are taken from a stationary landmark (CEJ) to the base of the defect; to the crest of bone, and to the apex of the longest root in millimeters. All measurements are taken parallel to the long axis of the tooth. The measurements are shown in Figures 8 a and b. A_0 is the root length at baseline, B_0 is the measurement from the CEJ to the base of the defect at baseline, and C_0 is the CEJ to the crest of the defect projected onto the root surface (Figure 8, left). At follow up, the A and B measurements are repeated (Figure 8, right).

Figure 8 Measurements on Radiographs at Baseline and 6 Months Post-surgery

Subsequent images are logged in and saved to the file. Linear measurements of bone height along root surfaces are made using the same method as the original defect. Bone height changes and percent bone fill estimates, based on loss or gain (resorption or osseous recontouring) of bone from baseline images are computed and entered onto the Independent Radiological Evaluation form (CRF 11).

Measurements to the root apex taken from baseline images are used to correct for any geometric distortion (elongation/foreshortening) of subsequent images and the percent of distortion (plus or minus) as well as percent of bone fill are computed using established formulae.

$$\text{Linear bone change} = B_0 - B_{fu}$$

$$\text{Percent bone fill} = (B_0 - B_{fu}) / (B_0 - C_0)$$

Note: It is not appropriate to include in the calculation of %BF the distance from the CEJ to the crest of the defect projected onto the root surface. If it were included, an increase in crest height would result in a decrease in the calculated %BF while a decrease would result in an increase in the calculated %BF.

8.1.4 Procedures for Clinical Laboratory Samples

Serum will be collected before the surgery at Visit 5 (Baseline), Visit 6 (2 weeks post-surgery) and Visit 7 (4 weeks post-surgery) in accordance with acceptable laboratory procedures. Subjects with an increase of specific antibody production against rh-bFGF will have blood serum collected for testing at subsequent follow-up visits until their results return to baseline values. The maximum volume of blood at any single visit is approximately 4 ml to isolate 2 ml of serum, and the approximate total volume of blood for the study is 12 ml. Details of these procedures, storage condition of the serum samples and shipping instruction will be given in the laboratory manual provided by [REDACTED]. The serum samples will be stored in a freezer at the site or a commercial laboratory. Within two weeks of the collection of the Visit 7 sample for a subject, all three samples for that subject will be shipped to the central laboratory. If serum is collected at subsequent visits, the site will ship each serum sample to the central laboratory within two weeks of its collection.

The central laboratory, [REDACTED], will perform ELISA assay for total serum antibody level of IgG, IgA and IgM for rh-bFGF upon receipt of the serum samples from investigational sites. The ELISA assay method will be established and validated by [REDACTED] before testing the clinical samples. If an increase in the rh-bFGF specific antibody level is detected in a serum sample, the neutralizing activity of the antibody will be measured. The site will be notified that an additional blood serum sample from that subject will be required at the next visit. The results of laboratory tests will be sent to the data management vendor. [REDACTED] will bank all serum samples until Sunstar notifies them that the FDA has reviewed and approved the assays.

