3.0 INTRODUCTION

3.1 Background

3.1.1 Investigational Device

The investigational device, [REDACTED] Growth Factor Enhanced Bone Graft Substitute (GFeBGS) as a “kit” product, consists of the synthetic bone graft substitute, β -tricalcium phosphate (β -TCP), saturated with reconstituted recombinant human basic fibroblast growth factor (rh-bFGF) in 1% hydroxylpropyl cellulose (HPC) solution. The β -TCP is supplied in a sterile particulate form in one container. All kits contain a sterile lyophilized cake in a vial. The kits with investigational products have rh-bFGF added to the lyophilized cake and the kits for the control product do not. The kits also contain a solvent, 1% HPC sterile solution, supplied in a sterilized prefilled syringe for reconstituting the lyophilized cake. The β -TCP is saturated with the reconstituted rh-bFGF/HPC or control solution immediately prior to application to the periodontal defect site during the periodontal surgical procedure. The investigational device would be appropriately regulated under 21 CFR §872.3930, “Bone Grafting Material, Dental, With Biologic Component”, Class III, Procode NPZ.

The investigational device was assessed for biocompatibility through pre-clinical studies. The studies have been conducted in a GLP compliant contract laboratory in the U.S.

3.1.2 β -TCP

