8.3.6 Visits 8 and 9: Subsequent Follow-up or Early Termination Evaluations

Subsequent follow-up visits occur at 3 and 6 months (final evaluation) post-surgery (\pm one week). During these visits, photographs are taken and the endpoint measurements of clinical attachment level (CAL), probing pocket depth (PD) and gingival recession (GR) will be assessed in the surgery site. Subjects with an increase of specific antibody production against rh-bFGF at Visit 7 will have blood serum collected until their results return to baseline values. Deep scaling of the target tooth should not be performed for the duration of the study and no additional implantation of the investigational product is allowed. Note that this visit is also conducted for early termination. Note that if a subject is diagnosed with a precancerous lesion such as leukoplakia after the study starts, it will be biopsied as appropriate for further analyses. A summary of all procedures to be performed is listed below:

Summary of Procedures/Measurements:

- Detailed probing measurements of the target tooth including:
 - CAL (calculation)
 - PD
 - GR
 - BOP
- Photographs of surgical site
- Routine supragingival prophylaxis
- Standardized PA radiograph of surgical site (see Section 8.1.3)
- Only at 3 months post-implantation: Oral hygiene instruction and full-mouth prophylaxis for staining due to CHX rinse or swab
- Record tobacco use on the Subsequent Follow-up Evaluation form (CRF 6)
- Concomitant medication review, especially number and type of analgesics since the last visit
- Complete the Subsequent Follow-up Evaluation form (CRF 6)
- Adverse Events review. Complete the Adverse Events form (CRF 8) if necessary
- If necessary, collect blood serum sample for rh-bFGF antibody

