12.1.3 Analysis Populations

Three populations will be considered in this study as follows.

Intent-to-Treat (ITT) population: The ITT population is defined as all randomized patients who receive the study therapy. All effectiveness analyses will be performed using the ITT population as randomized. The ITT population will be used for all primary effectiveness analyses.

Modified ITT (mITT) population: The mITT population is defined as all ITT patients who were eligible, received the study treatment as randomized (e.g. 0.3% GFeBGS when randomized to 0.3% GFeBGS), received the treatment as specified in the protocol, had at least one post-baseline evaluation, and maintained the evaluator treatment blind. The mITT population will be used for all confirmatory effectiveness analyses.

Safety population: The safety population is defined as all patients receiving any study therapy. Safety analyses will be based on the actual treatment administered. The safety population will be used for all safety analysis.

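### The request for an extra antibody sample tells the site which subjects had an rh-bFGF antibody rise, and nothing stated keeps that signal from the blinded examiner

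*Protocol*

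**What the plan says.** Section 8.1.4 of the Protocol has serum taken at Visit 5 (before surgery), Visit 6 (2 weeks) and Visit 7 (4 weeks). On shipment it says "Within two weeks of the collection of the Visit 7 sample for a subject, all three samples for that subject will be shipped". The central laboratory runs the ELISA "upon receipt of the serum samples from investigational sites". The trigger and its consequence are "If an increase in the rh-bFGF specific antibody level is detected in a serum sample", after which neutralizing activity is measured and "The site will be notified that an additional blood serum sample from that subject will be required at the next visit". The laboratory results themselves go to the data management vendor.

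Sections 4.2.3, 5.2.4 and 8.3.6 all tie further serum collection to an antibody rise. Section 8.3.6 lists the draw among the Visit 8 and 9 procedures ("If necessary, collect blood serum sample for rh-bFGF antibody"), in the same list as CAL, PD, GR and BOP.

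On treatment content, Section 3.1.1 says "The kits with investigational products have rh-bFGF added to the lyophilized cake and the kits for the control product do not". On blinding, Section 8.1 says "The Investigator and all study personnel will be blinded to the treatment", and the study design text in Section 1.0 keeps evaluating investigators blinded for the six months after surgery. The mITT definition in Section 12.1.3 includes only subjects for whom the study "maintained the evaluator treatment blind".

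**The concern.** The protocol gives one reason for an extra serum draw at Visit 8 or 9: an antibody rise. Anyone at the site who knows the protocol can therefore decode the request, or the sight of the draw. Since the control kit contains no rh-bFGF, a new rise makes an active arm more likely. The only separation the protocol states is between examiner and surgeon (Sections 8.1 and 8.2.1), and Section 8.1.2 names the Investigator among those who perform clinical examinations. A notice addressed to the site could thus reach the person who probes the tooth or rates causality.

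What is at stake is judgement-dependent data in a small trial. CAL is the sum of two hand-probed readings, and the Investigator rates the causal relation of each adverse event to the device (Sections 9.1.7 and 9.2.1.2). Expectation could shift either one, and mainly in the active arms. Dose selection under Section 12.1.10 rests on the composite that contains CAL.

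**Working it through.** The protocol states no figure on this point, so there is none to reproduce. The check has four parts.

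**1. Can the notice arrive before the examinations?** Inputs: Visit 7 at 4 weeks ±3 days (Section 8.3.5), shipment within two weeks of Visit 7 (Section 8.1.4), and Visits 8 and 9 at 12 and 24 weeks ±7 days (Figure 5, Section 8.3.6).

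- Latest shipment: 28 + 3 + 14 = day 45.
- Earliest Visit 8: 84 − 7 = day 77, leaving 77 − 45 = 32 days.
- Earliest Visit 9: 168 − 7 = day 161, leaving 161 − 45 = 116 days.

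If samples are assayed on receipt, the notice has time to arrive before both visits. Section 8.1.4 also has samples banked until the sponsor reports FDA review and approval of the assays. If that means a hold before testing, rather than retention after it, the notice could come later.

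**2. How much does the notice reveal?** Allocation is 1:1:1:1 (Section 12.1.2), so P(active) is 0.75 before any notice. With s the rate of detected rises in active arms and f the rate in control:

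P(active | notified) = 0.75·s / (0.75·s + 0.25·f)

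The rates below are assumptions; the protocol gives none.

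| f (control) | s (active) | P(active given notified) |
|---|---|---|
| 0 | any above 0 | 1.00 |
| 1% | 5% | 0.0375 / 0.0400 = 0.94 |
| 1% | 10% | 0.0750 / 0.0775 = 0.97 |
| 1% | 20% | 0.1500 / 0.1525 = 0.98 |
| 5% | 5% | 0.75 (no gain) |
| 5% | 10% | 0.0750 / 0.0875 = 0.86 |
| 5% | 20% | 0.1500 / 0.1625 = 0.92 |

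For subjects without a notice little changes: with s from 5% to 20% and f at 0 or 1%, P(active) is 0.71 to 0.74.

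**3. How many subjects?** With 20 evaluable per group, 60 are on active treatment. At s = 5%, 10% and 20%, 60·s = 3, 6 and 12 subjects, or an average of 1, 2 and 4 per active arm. In control, 20·f = 0.2 at f = 1% and 1 at f = 5%.

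**4. Which endpoints are exposed?**

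- The primary composite is assessed at six months only (Sections 4.2.1 and 5.2.2). Its CAL part is probed at the site. Its LBG part is measured at a reading center on coded images (Section 8.1.3.3) and is not exposed.
- Probing readings are rounded to whole millimetres (Section 8.1.2), so ΔCAL is a whole number. A gain of 2 mm meets the 1.5 mm threshold and a gain of 1 mm does not. A 1 mm difference in one reading can therefore decide the CAL criterion, but it decides the composite only where LBG is at least 1 mm.
- Where it does, one changed call in an arm of 20 is 1/20 = 5 percentage points. This gives the scale of a single call; it is not an estimate of bias.
- The 3- and 6-month ΔCAL, PDR and ΔGR and the 3-month BOP are secondary measures taken at the same visits.

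**The case against.** A reader might infer that the blind fails outright for antibody-positive subjects. The documents do not support that. The notice goes to the site, not expressly to the examiner, and says only that another sample is needed; results go to the data management vendor. Section 8.1.4 leaves details of the sample procedures to a laboratory manual that is not at hand, and routing rules may be there. What stands is that the protocol states no barrier.

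A reader might also take the primary endpoint to be exposed at both late visits and in full. It is not: the 3-month examination is secondary, and biased probing cannot create a success where the centrally read LBG falls short.

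The information gain is limited. Three subjects in four are on active treatment anyway, the notice carries nothing if rises are equally common in control, and it does not identify the dose, which is what the trial is meant to inform. The antibody rate could be close to zero.

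It is tempting to add that the mITT set would lose mainly active subjects. Nothing in the protocol says that an extra draw counts as losing the evaluator blind; the only unblinding act it describes is scratching off the seal (Sections 7.3 and 7.4). The ITT population is used for the primary analysis. The consequence is possible but speculative.

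Finally, this is a feasibility study that will not be used for labeling (Section 1.0). All of this lowers the weight of the point. None of it supplies the missing separation between the notice and the examiner.

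**Conclusion.** The point holds in a limited form. Followed as written, Sections 8.1.4 and 8.3.6 send the site a subject-specific signal that can suggest active treatment. Sections 1.0 and 8.1 require blinding, and nothing stated keeps the signal from the examiner or from whoever rates causality. The exposure is the CAL half of the 6-month composite, the secondary probing measures at 3 and 6 months, and adverse-event causality ratings.

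The size cannot be fixed from the document. The figures of 3 to 12 flagged active subjects, and a chance of active treatment of 0.86 to 1.00 for a flagged subject, rest on assumed rise rates of 5% to 20% in active arms and a lower rate in control. They also assume testing on receipt of the samples. This is an inexpensive improvement worth making, not evidence that the results would be biased.

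**What to change.** - **Sections 8.1.4 and 8.3.6:** send the extra-sample request only to an existing site staff member who neither performs the examinations nor rates adverse-event causality.
- **Section 8.3.6:** require the sample to be taken after the probing measurements and radiograph are recorded, out of the examiner's view. The draw is already last in the procedure list, but the list does not fix a sequence.
- **Section 12.1.3:** state that an antibody-triggered draw alone does not count as loss of the evaluator blind for mITT.

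The cost is protocol wording and minor routing and scheduling work at the sites. Antibody follow-up itself is unchanged. Drawing blood from every subject at Visits 8 and 9 would also hide the signal, but it adds a procedure for all and 2 × 4 = 8 ml to the stated total of about 12 ml. It is not recommended when routing achieves much of the same protection.

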8.1.5 Pregnancy

The safety impact of neutralizing antibody to rh-bFGF on fetuses has not been established by preclinical study. Therefore, any potential subject of childbearing potential will not be allowed to continue with the screening process. At screening (Visit 1), Investigators will ask female subjects about their child bearing potential and will exclude all who report a childbearing potential. If any subject has an unanticipated pregnancy after receiving the study treatment, it should be reported using a Protocol Deviation form (CRF 9) and the subject may remain in the study.

8.1.6 Documentation of Screening Failure

Investigators must account for all subjects who sign informed consent for screening at Visit 1 (Screening). If the subject is found to be not eligible prior to randomization, the Investigator should complete the Screening Failure Log.

Subject screening numbers assigned to subjects who fail screening should not be reused.

8.2 Examiner Calibration

8.2.1 Training of Surgeons, and Training of Examiners

One to two periodontists from each investigational site will be trained to perform the surgeries. One individual will be designated as the primary surgeon and should perform most of the procedures. The other individual will be the back-up and may also perform any non-examiner procedures when the primary clinician is not available. All surgeons must have ample experience in periodontal regenerative procedures and receive training. Surgeons will be trained on the surgical technique, end point of root debridement, handling and placement of test materials and suturing technique. To insure standardization of the surgical procedures, training will be conducted to thoroughly review all aspects of the pre-surgical, surgical and post-surgical phases of the trial. This training will be carried out prior to the beginning of the trial.

In addition, two examiners (dentists or hygienists) will be trained on baseline, interim and final evaluation measurements, exclusive of clinical photographs. The examiners should be different individuals from the surgeons. The same examiner, if possible, should perform all measurements on a particular subject, *i.e.* baseline, interim, and final evaluation measurements, exclusive of clinical photographs.

